The design of the study is a randomised clinical trial (that will be registered at clinicaltrials.gov). Breast cancer patients will be randomised into two groups (group 1: intervention or group 2: control). The patients will be randomized using the Efron's biased coin design. (Efron, 1971) Patients are stratified by duration of radiation therapy/intervention (3 weeks vs. 5 weeks), type of surgery (mastectomy vs. breast conserving surgery and axillary lymph node dissection vs. sentinel node biopsy), and chemotherapy sequence (none vs. sequential vs. concomitant chemotherapy). Randomisation occurs when the informed consent is signed by the patient. Patients need to be referred as eligible candidates by an MD and can give consent only following an intake conversation, giving all information concerning the trial by going through the informed consent with the patient. This design is shown in figure 2.

[figure not shown]

Figure 2: Design of the study.

8) Medical device

Andullation® technology is a horizontal vibration technique, with stochastically modulated vibrations. Lievens (2007) described Andullation® as “a new vibration therapy introduced for medical application approved by the TÜV Rheinland Belgium N.V. and FDA massage mattress VM9100RM”. The technology is build-in in a massage mattress. Several studies show that vibration (Prisby et al., 2008) and horizontal position (Nepal et al., 2012) in general have a positive influence on relaxation, without side effects. References concerning the technology can be found at <http://www.iaat.eu/science/>

The medical device has a CE-mark in classification Pc IIa, type bf with certificate number Z-18-051-P and identification No. 0633.

Composition and dosing

Group 1 (intervention group): 3 to 5-week Andullation® intervention* (depending on and as long as the duration of the radiation therapy) will be performed, 3 times a week for 20 minutes. Patients wear comfortable clothing. The position of the medical device is adapted to the body contours of the patient for an ergonomic position. The patient is lying in a relaxed position with hands posed next to the body on the lateral side of the mattress.

* <https://www.hhp.be/nl/producten/andumedic-3-professional>

Medical device: Andumedic® 3 Professional

Settings of the medical device: a combination of program 3, 8 and 18 (standardized)

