Group 2 (control group) will follow the same intervention protocol as group 1, but without the application of the Andullation® technology. Environmental parameters will be equal to those of group 1.

Producer/distributor

Producer:

International Association of Andullation® Technology (IAAT) - [name] (president dr. [name]) www.iaat.eu

Official dealer:

Home Health Product bvba (HHP) – [name] (CEO [name]) www.hhp.be

Packaging/storage conditions

Normal packaging, transport and storage conditions.

Known side effects

Up to now, there are no negative side effects reported about 20 minutes of Andullation® technology in literature or clinical experience. The Andullation® application is approved as a medical device by TÜV Rheinland Belgium N.V. and FDA massage mattress VM9100RM.

Pregnancy, epilepsy and a recent orthopaedic implant are contra indications reported by the producer and dealer.

Side effects will be registered during the trial.

9) The subjects:

Number of subjects

At the Department of Radiation Therapy of the UZ Brussel, an average of 8 breast cancer patients starts radiation therapy for about 3 to 5 weeks every week. Taking into account the sample size estimation/calculation, the duration of the project (Chair ‘Andullation Care Research’ of the VUB) and the availability of the medical device(s), we have constructed the inclusion schedule below (table 1).

The schedule is based on a 5-week intervention (and control) over a duration of 14 months to include 118 patients for the two study arms. If patients who have only 3 weeks of intervention are included, even more patients can be included. Therefore, insurance is based on the inclusion of maximum 130 patients, taking into account extra (3-week intervention) patients and a drop-out of 10%.

	M1/M2									start/2M	N = (op M14)
	W1	W2	W3	W4	W5	W6	W7	W8	W9		
1st week intervention	2	2	2	2	2	2	2	2	2	18	118
2nd week intervention		2	2	2	2	2	2	2	2		
3rd week intervention			2	2	2	2	2	2	2		
4th week intervention				2	2	2	2	2	2		
5th week intervention					2	2	2	2	2		
interventions/day	2	4	6	8	10	10	10	10	10		
	M13/M14										
	W53	W54	W55	W56	W57	W58	W59	W60	W61		
1st week intervention	2	2	2	2	2						
2nd week intervention	2	2	2	2	2	2					
3rd week intervention	2	2	2	2	2	2	2				
4th week intervention	2	2	2	2	2	2	2	2			
5th week intervention	2	2	2	2	2	2	2	2	2		
interventions/day	10	10	10	10	10	8	6	4	2		

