Questionnaire		- Distress Thermometer	- Brief Pain Inventory (BPI) - Numeric Pain Rating Scale (NRS)		- Pittsburgh Sleep Quality Index (PSQI) - Insomnia Severity Index (ISI)	- EORTC QLQ BR23

Measurement moment	Before, during and after each intervention	Baseline After each 3 rd intervention Follow-up	NRS: Before and after each intervention, Follow-up BPI: baseline, after each 3 rd intervention and follow-up	Baseline After 3 weeks After 5 weeks (if radiation lasts 5 weeks) Follow-up	Baseline After 3 weeks After 5 weeks (if radiation lasts 5 weeks) Follow-up	Baseline After 3 weeks After 5 weeks (if radiation lasts 5 weeks) Follow-up
--------------------	--	--	--	--	--	--

Table 2: Procedures of the study.

[figure not shown]

Figure 1: These measurements will be repeated in week 3 and if your radiation therapy has a duration of more than 3 weeks, these measurements will also be repeated in week 5.

Questionnaires

- Distress Thermometer
A questionnaire to evaluate in what extent the patient experiences complaints like distress and anxiety, on a visual thermometer. (Mitchell et al., 2007)

- EORTC QLQ BR23
A questionnaire designed to investigate the quality of life in breast cancer patients. (Michels et al., 2013)
- Brief Pain Inventory
This questionnaire was designed to investigate the extent of pain and the influence of it on quality of life. (Abahussin et al., 2018)
- Pittsburgh Sleep Quality Index (PSQI)
This questionnaire was designed to assess sleep quality, quantity and disturbance. (Beck et al., 2004)
- Insomnia Severity Index (ISI)
This questionnaire was designed to assess the severity, nature and impact of insomnia over the past two to four weeks. (Morin et al., 2011)

Body parameters

- ANSWatch®
A device measuring heart rate through skin sensors. With the information withdrawn, the device calculates heart rate variability. (Sun et al., 2011)
- Perometer®
A device measuring arm contours with the use of infrared light. It is an efficient, safe, painless and reliable method to examine arm volumes. (Adriaenssens et al., 2013)
- Bioimpedance
By using bioimpedance, body composition will be estimated. Patients have to stand on scale and hold on to a handgrip that is connected with the scale. A small current will determine the body composition and especially extracellular fluid. This is a painless and innocuous examination. (Seward et al., 2016)

11) Flowchart

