Inclusion (and intervention) will start from the moment we receive a positive advice of the Medical Ethical Comité and will last for 14 months. The project (VUB Chair) is assigned for 24 months in total. An MD will refer patients as potential candidates for the trial after screening of the inclusion criteria and during the intervention, there will always be at least one MD in the PR4 building. (cfr table 1 and figure 2)

12) Randomisation/blinding:

The patients will be randomized using the Efron's biased coin design. (Efron, 1971) Patients are stratified by duration of radiation therapy (3 weeks vs. 5 weeks), type of surgery (mastectomy vs.

breast conserving surgery and axillary lymph node dissection vs. sentinel node biopsy), and chemotherapy sequence (none vs. sequential vs. concomitant chemotherapy).

Blinding is not possible.

13) Prior and concomitant therapy:

The patients are allowed to use every medication needed for their treatment before, during and after the intervention.

Any medication that has an influence on HRV activity, sleep, stress, edema and pain are reported before intake in the trial and monitored throughout the study.

14) Study analysis:

Sample size calculation

Based on our calculation in G*Power (with a medium effect size of 0.5 and with a power = 0.8), the total sample size is 128.

[figure not shown]

Figure 5: Sample size calculation

Analysis of the samples and statistical analysis

The promotor and researcher of the VUB Chair will analyze the samples and do the statistical analysis.

For all statistical analyses, superiority will be based on a two-sided p-value < .05. All statistical computations use SPSS v. 20.0 (IBM Corporation, Somers, NY, 10589, USA). Descriptive statistics will be used to describe medical and demographic characteristics of the population. Normality and homogeneity for both groups will be calculated. The repeated measures ANOVA design will be used to evaluate the changes over time and between groups. Correlations between outcome measures will be calculated as well.

15) Quality control and quality assurance:

The researcher will be present when the intervention is given to install the patient, to start the intervention and to make sure that everything runs according to plan.

The researcher will also make sure that all settings are properly programmed and placed as indicated in the protocol prior to welcoming the patient. The researcher will use the same checklist before starting each intervention.

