Related to the quality control and assurance of the outcome measures:

- Each participant will have a form fill to list every data.
- All measurements are conducted by the same investigator and the same validated measurement instruments.
- All interventions are performed with the same medical device.

16) Publication policy:

Scientific and marginal publications will be possible within the academic freedom of the researchers and there are no restrictions concerning the other (industrial) partners of the VUB Chair.

A signed agreement of the Chair can be obtained at VUB TechTransfer ([name]) Contracts Administration [name].

17) All documents are confidential. These documents are only accessible to the treating doctor and to the persons concerned in the execution and control of this clinical study. The name and every information that could reveal patients' identity will not be used in publications arising from this study and will not be shared with third parties. The data will be processed according the principles imposed by the new European General Data Protection Regulation (GDPR), that is operative since May 25th 2018. In the context of the study certain personal data will be collected. We, [name] and [name], are responsible for the correct processing and the information duty that is required.

Of course, we are only allowed to use personal data for the scientific purposes described in the information consent document. It is possible that the data are seen by persons in countries that do not use the same norms in the field of legal protection of data as in the EU. In that case, we commit to ensure that the requirements of the European and Belgian legislation about the protection of personal data are respected.

Thereafter we would like to announce that, conform the relevant legislation, the data obtained in this study will be saved during at least 4 years. According to the GDPR there are

certain rights in the processing of the data. The data protection officer of the VUB can be contacted: [contact]

References:

All references related to Andullation® technology: <http://www.iaat.eu/science/>

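### Randomising when consent is signed puts the baseline values after allocation in an open trial, and nothing in the visible text keeps the arm unknown until they are recorded

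*Combined protocol and SAP*

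**What the plan says.** **Order of events.** Section 7 (Study design) states: "Randomisation occurs when the informed consent is signed by the patient". Before that it places only referral by a physician and the information step: patients "can give consent only following an intake conversation, giving all information concerning the trial by going through the informed consent with the patient". It names no outcome assessment in this sequence.

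**Timing of measurements.** In Table 2 (section 10) the schedule for stress is "Baseline After each 3 rd intervention Follow-up". The BPI, edema, sleep and quality-of-life measures also have a baseline. The table does not place any of these before or after randomisation. HRV, the primary outcome, has no separate baseline; it is taken "Before, during and after each intervention". The pain NRS is likewise first taken before the first session.

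**Knowledge of the arm.** Section 12 states: "Blinding is not possible". Under section 8 the control group "will follow the same intervention protocol as group 1, but without the application of the Andullation® technology", so the arm is plain by the first session at the latest. Section 15 adds: "All measurements are conducted by the same investigator and the same validated measurement instruments". It also has the researcher set up each patient and start the intervention.

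**Analysis.** Section 14 states: "The repeated measures ANOVA design will be used to evaluate the changes over time and between groups". It names no baseline-adjusted model.

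**The concern.** A baseline serves as a pre-treatment value only if allocation cannot influence it. Here a patient may rate her distress or pain for the first time when she could already know whether she will receive the device, and the investigator recording it could know too. Relief, disappointment, or a wish to please can then enter the starting value differently in the two arms.

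The analysis judges the device by change over time between groups, so an arm difference created at baseline can pass into that comparison. If controls report more distress on hearing their allocation and later settle, their improvement looks larger and a benefit of the device is hidden. If intervention patients rate their starting complaints higher, the error runs the other way. Once a patient has been allocated, a clean baseline cannot be recovered.

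**Working it through.** **1. Sequence.** Study-specific measurements need consent. Section 7 ties randomisation to the signature. Therefore every baseline value in Table 2 follows randomisation. For HRV and the NRS the first reading belongs to the first session, which follows allocation in any case. No visible section reverses this order, and none delays disclosure of the arm.

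**2. Exposure by outcome.**
- Distress and pain are current self-ratings and are the most exposed.
- Sleep and quality of life are self-rated but less exposed. Section 10 says the ISI looks back two to four weeks, a window that may largely predate allocation.
- HRV is read by an instrument, but section 6 says that stress lowers vagal activity, so an effect is plausible on the trial's own theory.
- Arm volume (infrared) and bioimpedance (small current) are little exposed.

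**3. The plan's own figure.** Section 14 gives effect size 0.5, power 0.8, two-sided 0.05 and N = 128. A two-sample t-test with equal arms needs 63.77, rounded up to 64 per arm, so 128 in total (power 0.801). The figure reproduces and this point does not change it.

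**4. What a shift does.** Let allocation news shift the baseline difference between arms by s (in SD), and let a fraction f of that shift remain at later visits.

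Bias of the change contrast = f·s − s = −s(1 − f)

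- f = 1 (persists equally): bias 0.
- f = 0.5, s = 0.2: bias 0.1 SD in size.
- f = 0 (fades fully): bias equal to s in size.

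**5. Illustration for f = 0.** Assumptions not in the documents: no true effect, equal SDs, 64 per arm, one baseline and one later value with correlation ρ. With z = s / [√(2(1 − ρ)) · √(2/64)], the rejection probability is Φ(−1.96 + z) + Φ(−1.96 − z). For s = 0.2 and ρ = 0.5, z = 0.2/(1 × 0.1768) = 1.131 and the result is 20.5%.

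| Shift s | Change score, ρ = 0.5 | Change score, ρ = 0.7 | ANCOVA, ρ = 0.5 | ANCOVA, ρ = 0.7 |
|---|---|---|---|---|
| 0.1 SD | 8.7% | 11.3% | 6.2% | 8.6% |
| 0.2 SD | 20.5% | 30.9% | 10.0% | 19.8% |
| 0.3 SD | 39.6% | 59.1% | 16.5% | 38.4% |

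The ANCOVA columns use bias ρ·s and SD √(1 − ρ²), so baseline adjustment reduces the problem without removing it. A comparison of later values alone stays at 5%. At ρ = 0.5 the noncentral t gives 20.2% and 39.1% for shifts of 0.2 and 0.3 SD. With the 59 per arm implied by the schedule of 118 in section 9, the normal approximation gives 19.2% and 37.1%.

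**6. Direction.** The excess rejections fall almost entirely on one side. If controls report 0.2 SD more distress at baseline, 20.1% of trials would reject in favour of control and 0.1% in favour of the device.

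**7. Loss of power.** With a true effect of 0.5 SD, ρ = 0.5 and a masking shift of 0.2 SD, the apparent effect is 0.5 − 0.2 = 0.3 SD. Power falls from 80% to about 39%.

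**The case against.** **The order is deduced.** The sentence on consent could be read as a precondition: no randomisation before consent. Figure 2 and the measurement figure in section 10 are not shown and may add detail. This stands as a caution. It does not remove the need for the text of sections 7 and 12 to state the order.

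**A reader might infer that each patient knows her arm when baseline is taken.** The documents do not say when she is told. That blinding is impossible means the arm cannot be masked during treatment; it does not mean the arm is disclosed at consent. What the text supports is that nothing prevents her or the investigator from knowing.

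**A reader might take 20% or 39% as the trial's false-positive rate, or as a risk of a spurious claim for the device.** Neither follows. The figures require the reaction to move baseline and then vanish, whereas in an open trial knowledge of the arm continues. In the example of more distressed controls, nearly all the excess rejections would favour control.

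**HRV is not a single change score.** Three sessions a week for 3 to 5 weeks give 9 to 15 sessions, each with its own pre-session reading. The first is one of many in the repeated-measures analysis, so the illustration does not carry over to the primary outcome as quantified.

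**Losses between consent and baseline.** Patients lost in that gap would be randomised without a baseline, but the documents give neither its length nor a loss rate. Nothing can be concluded about how large or how uneven such losses would be.

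**Conclusion.** The point holds as a weakness of sequence: on the visible text, baseline follows allocation in an unblinded trial with one investigator taking all measurements, and nothing protects it. It chiefly concerns self-rated distress and pain, which are secondary outcomes.

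The bias in the group-by-time contrast equals the part of any baseline shift that does not persist, from zero up to the full shift, in either direction. Its real size, direction and persistence are unknown, so the percentages show sensitivity and do not predict a bias. The conclusion rests on two premises: study measurements need consent, and the missing figures do not state a different order. This is a cheap improvement.

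**What to change.** Change sections 7 and 12 to state this order: after consent the patient completes all baseline questionnaires (including the NRS), arm volume, bioimpedance and a resting HRV recording; only then is she randomised and her arm disclosed, before the first session. State in section 14 that these values are the baseline in the analysis, and align Table 2.

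The stratification factors (duration of radiation therapy, type of surgery, chemotherapy sequence) are clinical facts, so nothing stated in the protocol requires allocation at the moment of signature.

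The cost is protocol wording, slightly later knowledge of the allocation, and one added resting HRV reading if the first pre-session reading cannot serve. The change protects the baseline only. Knowledge of the arm at later visits remains, as in any open trial, and a reporting shift that persists would then appear in the contrast rather than cancel, so it still needs to be acknowledged when self-rated outcomes are interpreted.

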Table 1: Inclusion schedule of the study.

Inclusion criteria

- Histological proven breast cancer, following breast cancer surgery
- Starting with adjuvant radiation therapy (with or without concomitant chemotherapy) for 3 to 5 weeks
- Age: older than 18 years
- Medical report (possibly for another hospital) is required with:
diagnosis: tumor type and time of 1st biopsy (if relevant)
proposed therapy (start and end dates of each treatment and treatment type)
- Patients have to be able to perform the intervention (laying supine on the mattress for 30', of which 20' intervention)
- A written informed consent has to be signed in the spoken language of the patient. (French, Dutch or English as well as the questionnaires)

Exclusion criteria

- Severe neurological, orthopaedic or rheumatic disorders of the lower or upper limbs which makes it impossible to lay on the mattress in supine position
- Cardiac disorders

- Early or synchronous malignancy
- Pregnancy or lactation
- Persons suffering from depression or illnesses who influence the mental health or wellbeing

Replacement of subjects

A drop-out of 10% was taken into account in the sample size calculation and inclusion schedule. Since we can prolong the intervention with a few weeks (the Chair is assigned for 24 months), we can have an extra medical device of the distributor during the study, we can include more than two patients a week at the UZ Brussel, because there are on average 8 patients starting radiation therapy every week, ... we will be able to anticipate for a bigger drop out.

Restrictions and prohibitions for the subjects

Provocation of vagal nerve activity minimal 24 hours before intervention will be registered prior to every intervention. The use of medication that influences pain sensation, fluid homeostasis, sleep hygiene and stress will be registered.

10) Procedures:

The measurements will be obtained and results will be analysed at the PR4 building of the Universitair Ziekenhuis Brussel, [name].

	Autonomic nervous system	Stress	Pain	Edema	Sleep	Quality of life
Outcome measure	Primary	Secondary	Secondary	Secondary	Secondary	Secondary
Measurement	Heart rate variability through skin sensor (ANSWatch®)			Volume measurement of the arms (Perometer®) for the evaluation of lymphedema Body composition (bioimpedance) for the evaluation of vascular edema		

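### Epilepsy and recent orthopaedic implant are listed as device contraindications in section 8 but are not among the section 9 exclusion criteria

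*Combined protocol and SAP*

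**What the plan says.** Section 8, under Known side effects, states: "Pregnancy, epilepsy and a recent orthopaedic implant are contra indications reported by the producer and dealer". It adds that side effects will be registered during the trial.

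Section 9 then gives the eligibility lists. Three exclusion items and one inclusion item bear on this point:

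- Exclusion: "Pregnancy or lactation".
- Exclusion: "Severe neurological, orthopaedic or rheumatic disorders of the lower or upper limbs which makes it impossible to lay on the mattress in supine position".
- Exclusion: "Persons suffering from depression or illnesses who influence the mental health or wellbeing".
- Inclusion: "Patients have to be able to perform the intervention", which the item itself explains as lying supine on the mattress for 30 minutes, 20 of them with the intervention running.

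On the route into the trial, section 7 says: "Patients need to be referred as eligible candidates by an MD and can give consent only following an intake conversation". It also says: "Randomisation occurs when the informed consent is signed by the patient". Section 11 describes the referral step as follows: "An MD will refer patients as potential candidates for the trial after screening of the inclusion criteria".

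**The concern.** The protocol itself reports three conditions in which the device is contraindicated, yet its eligibility rules turn away only one of them. Followed as written, the rules can admit a patient with epilepsy or a recent orthopaedic implant and allocate her to the device.

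What is at stake is participant safety. An MD or researcher who remembers section 8 may catch the case, but that relies on individual practice and not on a criterion. Registering side effects and having an MD in the building help only once sessions have begun. There is a lesser practical cost too: if a contraindication comes to light after allocation, only a device-arm patient would have to stop treatment, so the withdrawal would be one-sided and avoidable.

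**Working it through.** There is no figure in the plan to reproduce. The check sets the section 8 contraindications against every section 9 item, and then against every other step described before the first session.

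**Contraindications against the eligibility lists**

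| Section 8 contraindication | Named in section 9? | Nearest item | Does that item cover it? |
|---|---|---|---|
| Pregnancy | Yes | Pregnancy/lactation exclusion | Yes |
| Epilepsy | No | Limb-disorder exclusion; mental-health exclusion | Not the first: epilepsy is not a limb disorder. The second only if read broadly |
| Recent orthopaedic implant | No | Limb-disorder exclusion; ability-to-perform inclusion | Only when the patient cannot lie supine |

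Contraindications carried over: 1 of 3. Section 9 items: 6 inclusion + 5 exclusion = 11, of which 0 name epilepsy or an implant. The remaining exclusions (cardiac disorders; early or synchronous malignancy) are unrelated. The required medical report concerns tumour diagnosis and planned therapy, so it need not record either condition. Neither condition is mentioned anywhere else in the text available.

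**Other steps that might catch the patient**

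- *MD referral (sections 7 and 11).* Section 11 words this as screening against the inclusion criteria, which mention neither condition.
- *Intake conversation (section 7).* Described as going through the consent form. The consent pages are not in the text available.
- *Medication record before intake (section 13).* It covers drugs affecting HRV, sleep, stress, edema and pain. It might reveal treated epilepsy; it would not be expected to reveal an implant.
- *Pre-session checklist (section 15).* Used before each session and so after allocation. Its content is not given, and the adjoining sentence concerns device settings.

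None of these is stated to check for epilepsy or a recent implant.

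**Possible exposure of one such patient**

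- Allocation: two arms kept in balance by a biased coin, so the chance of the device is about 1/2.
- Sessions (section 8, Composition and dosing; 3 per week for 3 to 5 weeks): 3 × 3 = 9, up to 3 × 5 = 15.
- Time at 20 minutes per session: 9 × 20 = 180 minutes, up to 15 × 20 = 300 minutes.

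These are full-course figures. They assume that nobody notices the contraindication and that the patient completes treatment.

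**The case against.** The strongest reply is that the safety information has not been left out. The contraindications stand in section 8, immediately before the eligibility lists; an MD must refer each patient; the intake conversation is compulsory before randomisation; and the researcher attends to install the patient and start the session. Staff working from the protocol have the contraindications in front of them. The consent form, which is not in the text available, is a natural place to raise them, and a check at the first session would still come before exposure even though it comes after allocation. The mental-health exclusion is also loosely worded, and an MD could reasonably apply it to some patients with active epilepsy.

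Part of this stands. A check in the consent pages or Figure 2 cannot be ruled out, so high confidence belongs to the mismatch between sections 8 and 9 and not to a claim that nobody would check. For epilepsy, a broad reading of the mental-health item would close some of the gap. The 180 to 300 minutes is a maximum.

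It does not remove the point. A contraindication should not depend on stretching an item that names neither condition, and stretching that item to an implant is strained. Section 8's statement that no negative side effects are known for 20-minute sessions gives no data on contraindicated patients. Wording in the consent form would leave the section 9 criteria unchanged.

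**Conclusion.** The concern holds. Two of the three contraindications reported in section 8 are missing from the section 9 exclusions, and no step described in the available text is stated to check for them before randomisation. As written, a contraindicated patient can be allocated to the device.

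The size in practice is unknown. The documents give neither the prevalence of these conditions among the candidates nor a harm rate, and the number affected could be zero. The effect on the primary analysis is negligible. This should be fixed on safety grounds; nothing in the documents supports a graver rating.

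**What to change.** Add epilepsy and recent orthopaedic implant to the section 9 exclusion criteria, with the time window for an implant taken from the producer's instructions. Have the referring MD screen every candidate for both before consent is signed. Because randomisation happens at consent, this applies the rule equally to both arms and prevents one-sided withdrawals later.

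The cost is two exclusion lines, two items on the MD's screen, and a small loss of eligible patients whose size the documents do not allow one to estimate. Recruitment has some slack: section 9 reports an average of 8 breast cancer patients starting radiation therapy each week against 2 planned inclusions, and states that the weekly intake can go above two.

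### Table 1 as labelled yields 114 patients, not the stated 118; the total, or the week labels and the 14-month duration, need a minor correction

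*Combined protocol and SAP*

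**What the plan says.** Section 9 (Number of subjects) plans accrual "over a duration of 14 months to include 118 patients for the two study arms", on the basis of five weeks of treatment per patient. Table 1 sets this out by week. Its first block (M1/M2, W1 to W9) has two starts in each of nine weeks, and the row ends with the block subtotal and the overall total: "1st week intervention 2 2 2 2 2 2 2 2 2 18 118". The last block (M13/M14) carries the labels "W53 W54 W55 W56 W57 W58 W59 W60 W61", with two starts in each of W53 to W57 and none after. The blocks between are not printed.

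Section 11 says of inclusion, together with the intervention, that it "will last for 14 months".

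Three other statements bear on the figure. Section 9 says that "insurance is based on the inclusion of maximum 130 patients", a ceiling meant to cover additional three-week patients as well as 10% drop-out. Under Replacement of subjects it says: "A drop-out of 10% was taken into account in the sample size calculation and inclusion schedule". Section 14 gives the calculated total sample size as 128, for an effect size of 0.5 and power of 0.8.

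**The concern.** The week labels, the cell entries and the daily totals in Table 1 agree with one another, but the printed total does not follow from them. 118 is the only accrual figure given for the two arms, and section 9 says the schedule was built with the sample size calculation in view. If the schedule is run as drawn, it ends short of its own total before any patient drops out. It is then also further below the calculated 128 than the text suggests: 14 patients short rather than 10.

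**Working it through.** **Inputs.** From Table 1: two starts per week (both arms together), first start W1, last start W57, last sessions W61, 18 starts per nine-week block, 10 starts in the last block. From section 9: five weeks of treatment, 14 months, total 118. From section 14: d = 0.5, power 0.8, two-sided .05, N = 128. Assumption: W10 to W52 run at two starts per week, the only rate shown in any printed start week.

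**1. Trying to reproduce 118.** Six two-month blocks of 18 plus the last block's 10 give 6 × 18 + 10 = 118, an exact match. The document does not show its working, so this route is inferred.

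**2. Counting by the printed labels.**
- W1 to W9: 9 × 2 = 18
- W10 to W52: 43 × 2 = 86
- W53 to W57: 5 × 2 = 10
- Total: 18 + 86 + 10 = 114, that is 57 × 2

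The gap is 118 − 114 = 4 patients, and 4/118 = 3.4%.

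**3. Checking against the daily row.** Two starts a week with five weeks of treatment puts 2, 4, 6, 8, 10 patients on schedule in W1 to W5 and 10 in each week from then to W57. It then gives 8, 6, 4, 2 in W58 to W61. This is what the table prints in both blocks, so the cells support a last start in W57.

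**4. Where the 4 could come from.** Six nine-week blocks end at W54 (6 × 9 = 54), but the last block is labelled as starting at W53.
- If the labels are right, 6 × 18 + 10 counts W53 and W54 twice: 2 weeks × 2 = 4, exactly the gap.
- If the labels are wrong and the last block should be W55 to W63, starts run to W59 and 59 × 2 = 118 is right.

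**5. Testing the second reading against the duration.** 14 × 365.25 / 12 / 7 = 60.9 weeks. Sessions to W61 fit 14 months; sessions to W63 overrun it by about two weeks. Each reading therefore leaves one stated figure wrong.

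**6. Size in power.** The 128 reproduces as a two-sample t-test: 63.8, rounded up to 64 per arm, with no drop-out allowance. With the same test, before drop-out:

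| Total N | Per arm | Power |
|---|---|---|
| 114 | 57 | 75.4% |
| 118 | 59 | 76.8% |
| 128 | 64 | 80.1% |

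The miscount itself costs about 1.5 points.

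**7. The insured maximum.** 118 × 1.10 = 129.8, close to 130. From 114, the same step gives 125.4, and division by 0.9 gives 126.7. Both are below 130.

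**The case against.** The best defence is that Table 1 is a feasibility sketch and does not set the sample size. The number the plan calculates is 128, and no error in the table changes it. Section 9 also says that the intervention period can be prolonged by some weeks within the 24-month Chair, that another device can be obtained, and that weekly inclusion can exceed two because about eight patients start radiotherapy there each week. Three-week patients would add further room. Four patients are two more weeks at the planned rate. All of this stands, and it makes the gap easy to recover. It does not correct the stated figure: these are contingencies, offered mainly against a larger drop-out, and Table 1 uses none of them.

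A second objection is that the slip may lie in the labels and not in the total. That also stands. It moves the error from the total to the week labels and the 14 months but does not remove it.

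A reader might go further and infer that the insured maximum is wrong because it was built on 118. The documents do not support this. The product 118 × 1.10 lies close to 130, but that derivation is not stated, and it would leave no room for the extra three-week patients that the same sentence names. The ceiling still covers 114 with 10% added. Re-deriving it from 114 by that step would put it near 126, below the calculated 128, and so make the protocol worse.

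**Conclusion.** The point holds as a minor correction. On its printed labels Table 1 yields 114 patients, and the stated 118 can be kept only by running to W63, beyond the 14 months given in sections 9 and 11. The conclusion rests on two starts a week in the unprinted W10 to W52; it does not depend on how 118 was formed. Double counting of W53 and W54 explains the gap exactly but remains an inference.

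The direct effect is 4 patients and about 1.5 points of power. The power figures assume a simple two-group comparison, the test that reproduces 128, and not the repeated measures ANOVA named for the analysis.

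It might also be inferred that the required sample size is in error. It is not: 118 is the yield of a schedule, and the calculated 128 is untouched. What the recount does show is that the schedule falls below 128 on either count, even with no drop-out.

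**What to change.** Choose one of two corrections in section 9 and Table 1:

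- State N = 114 for the 61-week schedule as labelled; or
- Keep 118, relabel the last block W55 to W63 (last start W59, last sessions W63), and change the 14 months in sections 9 and 11 to match. The prolongation that section 9 already foresees allows this.

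In either case, reconcile the chosen figure with the 128 in section 14 and state the power the schedule delivers before drop-out: 75.4% at 114 or 76.8% at 118, against 80% at 128. While doing so, say where the 10% drop-out enters, since 128 reproduces without it. Leave the insured maximum of 130 as it is; a sentence giving its basis would be enough.

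The cost is protocol wording, plus two further weeks of sessions under the second option.
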